#### Trial Office (WCTU)

On receipt of an SAE Form, the Trial Office will arrange for the Chief Investigator to perform an independent assessment of relatedness. The Chief Investigator will also asses all related SAEs for expectedness. If the event is deemed unexpected (i.e is not defined as an expected event in Section 7.2.2) it will be classified as an Unexpected and Related SAE.

#### Reporting to the REC

The Trial Office will report all events that are categorised as Unexpected and Related SAEs to the REC within 15 days of receipt. Details of all Unexpected and Related SAEs will also be reported to Principal Investigators at recruiting sites.

#### DMEC

The independent DMEC will review all reported unexpected SAEs.

#### 7.2.4. Reporting Period

Details of all related SAEs (except those listed in Section 7.2.2) will be documented and reported from randomisation until 12 months post randomisation. This reporting period should be sufficient to capture all SAEs associated with the trial protocol however, if a related SAE is identified after this period, the event should be reported to the Trial Office.

#### 8. DATA HANDLING

#### 8.1. Data Collection Tools

The Case Report Form (CRF) will comprise a set of forms capturing details of eligibility, baseline characteristics, treatment and outcome details. This trial will use an electronic data capture (EDC) system which will be used for completion of the CRF. Access to the EDC system will be granted to approved site personnel via the Trial Office. If the use of a paper CRF is required, then original forms should be sent to the co-ordinating team at WCTU and copies retained on site. CRFs are expected to be completed within 4 weeks of their due date.

Data reported on each form should be consistent with the source data or the discrepancies should be explained. If information is not known, this must be clearly indicated on the form. Missing and ambiguous data will be queried in line with the WCTU data management plan, which will outline the requirements for CRF completion and return.

Participant reported outcomes will be captured via a series of participant questionnaires (outlined in Section 3.2), combined into one questionnaire booklet. Paper questionnaire booklets will be issued to participants at the required time points by WCTU. Participants will complete their responses within the questionnaire booklet, and return the completed document to WCTU, for entry onto the trial database. Any sensitive disclosures reported via participant questionnaires will be appropriately managed in accordance with the University of Warwick's SOPs.

#### 8.2. Source Data

Source documents are where data are first recorded, and from which participants' CRF data are obtained. These include, but are not limited to, hospital records (from which medical history and previous and concomitant medication may be summarised into the CRF), clinical and office charts, laboratory and pharmacy records, diaries, microfiches, radiographs, and correspondence.

CRF entries will be considered source data if the CRF is the site of the original recording (e.g. there is no other written or electronic record of data). All documents will be stored safely in confidential conditions. On all trial-specific documents, other than the signed consent, the participant will be referred to by the trial participant number, not by name.

Investigators should keep records of all participating patients, all original signed informed consent forms and copies of any paper CRFs. It is necessary for investigators to provide access to source document for monitoring and audit purposes to WCTU, Sponsor, any monitoring or regulatory authorities as deemed necessary.

#### 8.3. Data Handling and Record Keeping

The database will be developed and managed by the Programming Team at WCTU and all specifications (i.e. database variables, validation checks, screens) will be agreed between the programmer and appropriate trial staff. The database will meet industry standard security criteria and only be accessible to authorised personnel. Within the database, participants will be identified by the trial participant number only.

All essential documentation and trial records will be stored by WCTU in conformance with the applicable regulatory requirements and access to stored information will be restricted to authorised personnel.

#### 8.4. Access to Data

Direct access will be granted to authorised representatives from the Sponsor, the WCTU monitoring team, host institution and the regulatory authorities to permit study-related monitoring, audits and inspections.

#### 8.5. Archiving

At the end of the study, following completion of the end of study report, UHDB and WCTU will securely archive all centrally held study related documentation for a minimum of 10 years. At the end of the defined archive period arrangements for confidential destruction will be made. It is the responsibility of each PI to ensure that data and all essential documents relating to the study are retained securely for a minimum of 10 years after the end of study, and in accordance with national legislation. WCTU will notify sites when study documentation held at sites may be archived, and then destroyed. All archived documents must continue to be available for inspection by appropriate authorities upon request.

## 9. RADIOTHERAPY QUALITY ASSURANCE

The radiotherapy quality assurance (RT QA) component of the trial will be coordinated by the National Radiotherapy Trials Quality Assurance (RTTQA) Group. The RT QA process will include prerecruitment and on-trial QA, details of which can be found in the accompanying RT QA planning and delivery guidelines. The RT QA guidelines are to be used in conjunction with the main trial protocol.

All participating sites must undergo the RT QA process and QA approval is required before participant recruitment can begin. Any queries regarding the RT QA process can be directed to the RTTQA team: [contact].

## **10. STATISTICS AND DATA ANALYSIS**

A detailed statistical analysis plan (SAP) will be drafted by the trial statistician. The SAP will be finalised and approved by the CI and an independent statistician before the final data analysis.

#### **10.1. Sample Size Calculation**

Five-year disease free survival (DFS) for participants with node negative disease after NACT was around 80% based on the pooled analysis published by von MG et al [6]. With advanced drug treatment

and improved outcome over time we would anticipate higher rates of DFS to be seen today and thus the DFS in the control arm was estimated to be 90%. Thus, assuming five years recruitment and minimum of 4.5 years follow-up, recruiting 950 participants in each trial arm (1900 in total) would have the ability to demonstrate non-inferiority of omitting further axillary treatment, defining non-inferiority as 'no worse than 3.5%' below the control arm 5-year DFS with a 5% 1-sided significance level and 85% power, allowing for 7% non-collection of primary outcome data using the POWER procedure within the SAS statistical software.

Lymphoedema is a potential side effect of further axillary treatment and hence is considered as a coprimary endpoint. The AMAROS trial reported five year lymphoedema rates for ALND of 23% (76/328) and 11% (31/286) for ART [24] based on clinical signs of lymphoedema. A meta-analysis reported a lymphoedema rate for sentinel-node biopsy of 6% [3]. A minimum 5% important difference in the proportion of participants with lymphoedema is acceptable as defined by discussions with the clinicians, the PPI group and patient co-investigators. Any differences larger than this would provide stronger evidence and have a bigger impact on clinical practice. Thus assuming similar lymphoedema rates within this trial and the majority of participants randomised to standard axillary treatment had ART (rather than ALND) then a trial of 1900 participants would have 90% power to detect at least a 5% difference between trial arms if the overall lymphoedema rate in the control arm was 11%, with a 2sided significance level and allowing for 25% dropout. The allowance for attrition is greater as the outcome is participant-reported from questionnaires. The power would be higher to detect the larger differences between trial arms that would be expected with increasing use of ALND in the standard axillary treatment arm (see Table 1).

Table 1: Sample sizes for the proportion of participants self-reporting lymphoedema symptoms at 5 years using a 5% two-sided significance level and 90% power

Proportion in	Proportion in	Difference	Sample size	Total sample	Allowing for
control arm	no axillary		in each arm	size	25% dropout
(axillary	treatment				
treatment)	arm				
11	6	5	691	1382	1846
12	6	6	509	1018	1360
13	6	7	395	790	1054
14	6	8	319	638	852
15	6	9	264	528	704

Additionally, the sample size is sufficient to demonstrate non-inferiority of omitting further axillary treatment in the secondary outcome of axillary recurrence free interval (ARFI) with 90% power and a 5% 1-sided significance level, defining non-inferiority as 'no worse than 2%' below the control arm 5-year ARFI of 98% using the POWER procedure within the SAS statistical software.

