## 3. AIMS, OBJECTIVES AND OUTCOME MEASURES/ ENDPOINTS

## 3.1. Objectives

The *primary objectives* are to assess whether, omitting further axillary treatment (either ALND or ART) for patients with early stage breast cancer and axillary nodal metastases on needle biopsy, who after NACT have no evidence of residual cancer in the lymph nodes on SNB, is non-inferior to axillary treatment in terms of disease free survival (DFS), and reduces the risk of lymphoedema at five years.

Secondary objectives are:

- I. To compare arm morbidity and quality of life between and within the two allocated groups over five years.
- II. To compare axillary recurrence free interval, breast or chest wall recurrence, regional (nodal) recurrence, distant metastasis, and overall survival, contralateral breast cancer, non-breast malignancy between the two allocated groups over five years.
- III. Economic evaluation

- a. To compare costs to the NHS and to participants over five years
- b. To compare quality-adjusted life years (QALYs) over five years.
- c. To estimate cost-effectiveness measured in terms of incremental cost per disease free interval from the perspective of the NHS and patients over five years
- d. To estimate cost-effectiveness measured in terms of incremental cost per lymphoedema event avoided from the perspective of the NHS and patients over five years
- e. To estimate cost-effectiveness measured in terms of incremental cost per QALY gained from the perspective of the NHS and patients over five years
- f. To extrapolate costs and outcomes over the lifetime of patients with early stage breast cancer and estimate the cost-effectiveness measured in terms of incremental cost per QALY gained from the perspective of the NHS and patients
- IV. Qualitative Evaluation
  - a. To identify and investigate recruitment issues and develop effective and realistic strategies to ensure overall success of the trial

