#### 6.3.3. Method of Implementing the Treatment Arm Allocation

Randomisation will be performed by computer using a minimisation algorithm, stratified by the following variables:

- institution
- type of breast surgery (BCS or mastectomy)
- receptor status (triple negative, HER2+, ER/PR+ and HER2-)

The randomisation system will ensure that there is no bias between the two trial groups. Participants will be randomised strictly sequentially, and allocation between trial arms will be in a 1:1 ratio. The computer minimisation programme will be developed and held centrally at the WCTU.

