#### 10.3.3. Statistical Methods

Time to event outcomes, including the co-primary outcome of DFS, will be assessed using Kaplan-Meier curves and compared using Cox proportional hazards models. Hazard ratio (forest) plots will be constructed for the stratification variables and important prognostic factors. A sensitivity analysis will be carried out adjusting for stratification variables (institution, type of breast surgery, receptor status). Exploratory subgroup analyses will be performed for those having ALND or ART.

The proportion of patients experiencing lymphoedema at five years will be compared across trial arms using a chi-squared test and a logistic regression model used to adjust for stratification variables. Arm morbidity, arm function and QoL will be scored using the appropriate manuals and assessed using a longitudinal mixed model regression analysis if model assumptions valid or a standardised area-under-the-curve analysis. Consideration will be given to any missing data in the form of a sensitivity analysis to determine the degree to which the conclusions may change with different missing data assumptions and mechanism models.

All analyses will be carried out on an intention-to-treat basis to preserve randomisation, avoid bias from exclusions and preserve statistical power. Thus, all subjects randomised into the study regardless of whether they receive the study intervention will be analysed unless they withdrew consent for further follow-up. The success of no axillary treatment relies on the confirmation of both non-inferiority in DFS and at least a 5% reduction in the proportion of participants with lymphoedema. No adjustment for multiple testing has been incorporated.

A Statistical Analysis Plan (SAP) will be developed to provide full details of the planned analysis.

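### The 90% power stated for non-inferiority in axillary recurrence free interval is not the power of the Cox comparison the protocol names, which is about 80% (79–84%) if both arms are at 98%

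*Protocol*

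**What the plan says.** The last paragraph of section 10.1 makes a separate powered claim for ARFI, on these terms: "with 90% power and a 5% 1-sided significance level, defining non-inferiority as 'no worse than 2%' below the control arm 5-year ARFI of 98" per cent. It credits SAS PROC POWER. It does not name the test, the ARFI assumed in the experimental arm, the expected number of events or a hazard-ratio margin.

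The design inputs come earlier in the same section: "Thus, assuming five years recruitment and minimum of 4.5 years follow-up, recruiting 950 participants in each trial arm (1900 in total"). The 7% allowance for missing data there is stated for the primary outcome only. Section 6.3.3 says "allocation between trial arms will be in a 1:1 ratio".

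On analysis, section 10.3.3 says: "Time to event outcomes, including the co-primary outcome of DFS, will be assessed using Kaplan-Meier curves and compared using Cox proportional hazards models". Section 3.2.2 defines ARFI as a time from randomisation to axillary recurrence or censoring, so this sentence covers it. No other ARFI comparison is described.

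**The concern.** The margin is written as a difference in 5-year percentages, while the only named comparison works on the hazard ratio. With a 2% event rate, the power of a hazard-ratio test depends on a small number of events. If the arms are equal, both contribute events at the low control rate, and the total falls short of what 90% power requires.

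ARFI is the outcome closest to the clinical question of whether disease returns in an untreated axilla, and the sponsor gave it a margin, an alpha and a power. If the Cox comparison decides it, truly equal arms would fail to show non-inferiority about 16–21% of the time, against the 10% implied.

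**Working it through.** **Inputs.** From section 10.1: control 5-year ARFI 98%, margin 2 points (so 96%), one-sided alpha 5%, 950 per arm, 5 years of recruitment, minimum follow-up 4.5 years. Assumptions: exponential event times, uniform accrual, proportional hazards. Loss is shown at 7% (883.5 per arm) and at 0%, because none is stated for ARFI.

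**Formulas.** With λ = −ln(S5)/5 and minimum follow-up a, the probability of an observed event is p = 1 − [exp(−λa) − exp(−λ(a+5))]/(5λ). Power for d events against hazard-ratio margin M is Φ(½√d · ln M − 1.645) (Schoenfeld).

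**1. Reproduce the printed 90%.** With a = 4.5, p = 0.0279 at 98% and 0.0555 at 96%.
- Log-rank set-up, 98% v 96%, 7% loss: events = 883.5 × (0.0279 + 0.0555) = 73.6; power 91.5% (89.5% by Freedman's formula).
- Non-inferiority of two 5-year proportions, both 98%, 7% loss: SE = √(2 × 0.98 × 0.02/883.5) = 0.00666; 0.02/0.00666 − 1.645 = 1.36; power 91.3% (92.9% without loss).

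Both routes land near 90%. DFS helps to separate them. The first set-up at 90% v 86.5% with 7% loss gives p = 0.1367 and 0.1830, hence 883.5 × 0.3198 = 282.5 events. At a hazard ratio of ln(0.865)/ln(0.90) = 1.376 that is 85.1% power. Sections 10.6 and 10.1 print 282 events and 85%. The first route is therefore the likelier origin of the ARFI figure too.

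**2. Margin and events needed for Cox.** M = ln(0.96)/ln(0.98) = 0.04082/0.02020 = 2.02, ln M = 0.703. Events for 90% power = 4 × (1.645 + 1.282)²/0.703² ≈ 69 (76 by Freedman).

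**3. Events and power with 98% in both arms.** For a = 5, p = 0.0298.

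| Follow-up | Loss | Events | Cox power |
|---|---|---|---|
| 4.5 to 9.5 years | 7% | 2 × 883.5 × 0.0279 = 49.2 | 79.5% |
| 4.5 to 9.5 years | 0% | 2 × 950 × 0.0279 = 53.0 | 82.0% |
| 5 to 10 years | 7% | 2 × 883.5 × 0.0298 = 52.7 | 81.8% |
| 5 to 10 years | 0% | 2 × 950 × 0.0298 = 56.7 | 84.2% |

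Simulated Cox fits (4000 per scenario) for the first two rows gave 78.9% and 82.1%. Treating other DFS events as competing censoring lowers those rows to about 77% and 80%.

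**4. The alternative on the margin's own scale.** Simulating the Kaplan-Meier difference at 5 years (5000 runs, 7% loss) gave 90.4% power with both arms at 98%. With the experimental arm at a true 96%, false non-inferiority was 5.1%. It was 5.7% when a further 7% loss by 5 years was assumed.

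**The case against.** **The gap could be read as much larger.** Section 3.1 frames the secondary comparisons as running over five years. A reader might infer that all participants are censored then, which would leave 35 to 38 events and 67–70% power. The protocol sets no such cut. Section 3.2.2 runs ARFI to the censor date, section 6.5.2 collects annual data until everyone has at least five years, and Appendix 2 schedules annual follow-up to month 120. The 67–70% is therefore only a conditional figure.

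**The 90% could be read as a proportions test paired with the wrong analysis.** That route does reproduce it. The log-rank route reproduces it equally well, and the same set-up also returns the DFS figures. The documents do not settle which was used, but they favour the log-rank route.

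**Loss and follow-up may be kinder than assumed.** This stands. The 7% is not stated for ARFI, and the study summary and section 13 point to at least five years of follow-up rather than 4.5. Both are allowed for in the table. If follow-up ran on until 282 DFS events with equal arms, there would be about 58 ARFI events and about 85% power, still below 90%.

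**The choice of test belongs in the SAP.** This stands in part. The protocol gives no hazard-ratio margin (2.02 is a conversion), and it names Kaplan-Meier curves as well as Cox models, so a Kaplan-Meier test would be compatible with section 10.3.3. But a power figure and a method of comparison are both printed here, and they do not agree. That goes beyond an omitted detail.

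**Conclusion.** The point holds as a wrong stated power on a secondary endpoint. Under exponential event times, uniform accrual and a true 98% in both arms, the Cox comparison has about 79–84% power, a shortfall of some 6–11 points against the printed 90%. The range reflects 0% or 7% loss and a minimum follow-up of 4.5 or 5 years.

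Counting events at 98% v 96% places the experimental arm at the margin, where non-inferiority should be concluded only about 5% of the time. An event total from that scenario does not apply when the arms are equal.

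A reader might infer that the trial is undersized or that its conclusion is at risk. The ARFI point does not support that. Section 10.1 presents ARFI as an additional capability of a sample sized for other outcomes, and section 10.3.3 defines success by DFS and lymphoedema alone.

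**What to change.** Choose one of the following before the SAP is finalised.

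- **Keep Cox as the deciding analysis.** In section 10.1 replace the 90% with about 80% (79–84% depending on loss and minimum follow-up), and state the hazard-ratio margin of 2.02, the expected events and the assumption of 98% in both arms. The cost is only a lower printed power.
- **Decide on the scale of the margin.** In section 10.3.3 state that ARFI non-inferiority is concluded if the one-sided 95% upper confidence limit for the Kaplan-Meier difference in 5-year ARFI (control minus no axillary treatment) is below 2 percentage points, with the Cox hazard ratio as supporting. This supports about 90% power. The cost is that recurrences after year 5 do not count in the deciding test: about 14 of the 49 expected events with 7% loss (49.2 − 35.3). Type I error may also run slightly above 5% with so few events.

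Either change takes a sentence or two and needs no extra participants, data or visits.

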## **10.2. Planned Recruitment Rate**

ATNEC will randomise 1900 participants from approximately 100 centres across the UK over 5 years. Based on a survey of UK practice, it is anticipated that each hospital will recruit five participants per year. A 50% participant uptake rate of those eligible is assumed.

An 18-month internal feasibility phase has been incorporated into the trial to assess the willingness of clinicians and patients to participate. The criteria for progressing from the internal feasibility phase at 18 months to the main trial are based on site opening, recruitment and compliance to allocated intervention and use a traffic light system of green for continuing to recruit, amber for considering amending the trial to improve recruitment either in terms of relaxing the eligibility, extending the number of sites and red for considering stopping the trial if there are no possible recovery options.

## **10.3. Statistical Analysis**

## 10.3.1. Stratification

Participants will be stratified by the following factors:

- Institution
- Type of breast surgery (BCS vs mastectomy)
- Receptor status (triple negative vs HER2 positive vs ER status positive or PR status positive and HER2 negative)

#### **10.3.2.** Summary of Baseline Data and Flow of Patients

Descriptive statistics will be presented to summarize the distribution of baseline variables across each of the randomisation groups. Continuous baseline variables will be reported with means and 95% confidence intervals (95% CI), if normally distributed, otherwise will be reported with medians and Interquartile Ranges (IQR). Categorical variables will be reported with frequencies and percentages.

A Consolidated Standards of Reporting Trials (CONSORT) flow diagram will be produced, showing the frequency of patients/ participants:

- Assessed for eligibility or confirmed as eligible,
- Excluded before randomisation (and the frequency of each reason for exclusion),
- Randomised,
- Allocated to each randomisation group,
- That received each allocated intervention,
- That did not receive each allocated intervention,
- Lost to follow-up (and the frequency of each reason for loss to follow-up) for each randomisation group,
- Analysed for each randomisation group,
- Not analysed (and the frequency of each reason for not being analysed) for each randomisation group.

#### 10.3.3. Statistical Methods

Time to event outcomes, including the co-primary outcome of DFS, will be assessed using Kaplan-Meier curves and compared using Cox proportional hazards models. Hazard ratio (forest) plots will be constructed for the stratification variables and important prognostic factors. A sensitivity analysis will be carried out adjusting for stratification variables (institution, type of breast surgery, receptor status). Exploratory subgroup analyses will be performed for those having ALND or ART.

The proportion of patients experiencing lymphoedema at five years will be compared across trial arms using a chi-squared test and a logistic regression model used to adjust for stratification variables. Arm morbidity, arm function and QoL will be scored using the appropriate manuals and assessed using a longitudinal mixed model regression analysis if model assumptions valid or a standardised area-under-the-curve analysis. Consideration will be given to any missing data in the form of a sensitivity analysis to determine the degree to which the conclusions may change with different missing data assumptions and mechanism models.

All analyses will be carried out on an intention-to-treat basis to preserve randomisation, avoid bias from exclusions and preserve statistical power. Thus, all subjects randomised into the study regardless of whether they receive the study intervention will be analysed unless they withdrew consent for further follow-up. The success of no axillary treatment relies on the confirmation of both non-inferiority in DFS and at least a 5% reduction in the proportion of participants with lymphoedema. No adjustment for multiple testing has been incorporated.

A Statistical Analysis Plan (SAP) will be developed to provide full details of the planned analysis.

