#### 3.2. Outcome

#### 3.2.1. Co-primary outcomes:

- Disease-Free Survival (DFS); defined and calculated as the time from randomisation until the date of first event of either a loco-regional invasive breast cancer relapse, distant relapse, ipsilateral or contralateral new invasive primary breast cancer or death by any cause or the censor date.
- Lymphoedema is self-reported based on two items from the validated Lymphoedema and Breast Cancer Questionnaire (LBCQ) (arm "swelling now" and arm "heaviness in the past year"). These items have been shown to be predictive of arm swelling of a 2 cm or more change in arm circumference, but provide a simpler patient-friendly measure which has been used in other studies [17-19]. Lymphoedema will be defined as 'yes' to both questions at five years.

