#### 3.2.2. Secondary outcomes:

- Arm function will be assessed using the shortened version of the Disability of the Arm, Shoulder and Hand (DASH), the 11-item QuickDASH questionnaire [20].
- Pain intensity and characteristics will be measured using questions from the Douleur Neuropathique (DN4) and Pain Numeric Rating Scale (NRS) and will relate to the areas affected by surgery and cancer treatment.
- Axillary recurrence free interval, calculated from the date of randomisation to the date of axillary
  recurrence or the censor date. Axillary recurrence is defined as pathologically (cytology or
  biopsy) and/or radiologically confirmed recurrence in lymph nodes draining the primary tumour
  site, i.e. nodes in the ipsilateral axilla, infraclavicular fossa, supraclavicular fossa and
  interpectoral area. The date of axillary recurrence is the date on which imaging or pathology
  report (whichever comes first) confirms axillary recurrence.
- Overall survival; calculated as the time from randomisation until the date of death by any cause or the censor date.
- Local (breast or chest wall) recurrence is defined as pathologically (cytology or biopsy) and/or
  radiologically confirmed recurrence after mastectomy in the skin or soft tissue of the chest wall
  within the anatomical area bounded by the mid-sternal line, the clavicle, the posterior axillary
  line and the costal margin or any type of breast carcinoma in the breast after conservation

therapy. The date of local recurrence is the date on which the imaging or pathology report (whichever comes first) confirms local recurrence.

- Regional (nodal) recurrence is defined as pathologically (cytology or biopsy) and/or radiologically confirmed recurrent tumour in the lymph nodes in the ipsilateral axilla, infraclavicular, supraclavicular fossa, interpectoral area or ipsilateral internal mammary chain. The date of regional recurrence is the date on which the imaging or pathology report (whichever comes first) confirms local recurrence.
- Distant metastasis is defined as confirmed metastasis (positive pathology and/or definitive evidence on imaging) in all other sites of recurrence and may include those classified as: softtissue category, visceral category, central nervous system and skeletal spread. The date of distant metastasis is the date on which the imaging or pathology report (whichever comes first) confirms metastasis.

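### Kaplan-Meier for axillary recurrence free interval, with deaths censored by implication, slightly overstates the actual risk of axillary recurrence; report cumulative incidence with death as a competing event

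*Protocol*

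**What the plan says.** Protocol section 10.3.3 gives one method for every outcome measured as time to an event: "Time to event outcomes, including the co-primary outcome of DFS, will be assessed using Kaplan-Meier curves", with the arms "compared using Cox proportional hazards models". It makes no exception for outcomes in which death is not an event, and the protocol mentions neither competing risks nor cumulative incidence.

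Section 3.2.2 defines the interval as "Axillary recurrence free interval, calculated from the date of randomisation to the date of axillary" "recurrence or the censor date". It therefore has two possible ends, and death is neither of them. The contrast with disease free survival (DFS) in section 3.2.1 is plain, since that definition runs to "contralateral new invasive primary breast cancer or death by any cause or the censor date". Overall survival likewise counts death from any cause. The term censor date is not defined anywhere in the protocol.

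Section 10.1 gives ARFI its own non-inferiority statement on an absolute scale, "defining non-inferiority as 'no worse than 2%' below the control arm 5-year ARFI of 98" per cent, "with 90% power and a 5% 1-sided significance level". Section 10.3.3 leaves full analysis detail to a statistical analysis plan, which is not at hand.

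**The concern.** A participant who dies without an axillary recurrence cannot have one later. If such a participant is censored, Kaplan-Meier treats them as still at risk and as represented by those who remain. One minus the curve then estimates the risk in a population in which nobody dies, not the proportion of participants who have the event.

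For DFS and overall survival this does not arise, because death is an event. For ARFI it does. The protocol states its target as a five-year percentage, and an absolute percentage is the quantity that the choice of estimator changes. ARFI is also the outcome closest to the clinical question of leaving the axilla untreated, so its absolute risk is likely to be reported to patients. At stake is the accuracy of that figure, chiefly in later follow-up, and not the trial's main conclusion.

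**Working it through.** **The plan's own figure first.** Inputs from section 10.1: control ARFI 98% at five years, margin 2 points (96%), one-sided 5%, 90% power, 950 per arm, five years of recruitment, minimum follow-up 4.5 years. The 7% non-collection stated there for DFS is applied here too.

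- Hazard ratio at the margin: ln(0.96)/ln(0.98) = 2.02.
- Events needed (Schoenfeld): 4 × (1.645 + 1.282)² / (ln 2.02)² ≈ 69.2, so 70.
- Events expected with constant hazards, uniform accrual, one arm at 98% and one at 96%: 883.5 × (0.0279 + 0.0555) ≈ 73.6, where 883.5 = 950 × 0.93. Power 0.915.

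The stated 90% reproduces to within 2 points. The same way of counting gives 282.5 DFS events against the 282 in section 10.6. Counting events with both arms at 98% would give 49.2 events and power of 0.79; that is a separate matter from the estimator discussed here.

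**Kaplan-Meier against cumulative incidence.** The protocol gives no mortality figure, so I assume 5% to 10% dead by five years. Every death is a DFS event or follows one, so the planned 90% control-arm DFS caps five-year mortality in that arm at 10%. Hazards are constant and deaths are independent of axillary recurrence.

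- Axillary recurrence hazard: a = −ln(0.98)/5 = 0.00404 per year.
- Death hazard: m = −ln(0.95)/5 = 0.01026, or −ln(0.90)/5 = 0.02107.
- Kaplan-Meier complement: 1 − exp(−a·t).
- Cumulative incidence: a/(a + m) × [1 − exp(−(a + m)·t)].

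Control arm:

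| Time | Dead by 5 years | 1 − KM | Cumulative incidence | Excess, points | Relative excess |
|---|---|---|---|---|---|
| 5 years | 5% | 2.000% | 1.950% | 0.05 | 2.6% |
| 5 years | 10% | 2.000% | 1.899% | 0.10 | 5.3% |
| 9.5 years | 5% | 3.766% | 3.589% | 0.18 | 4.9% |
| 9.5 years | 10% | 3.766% | 3.415% | 0.35 | 10.3% |

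The 9.5 years is the longest follow-up at the planned final analysis (5 + 4.5).

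**Difference between arms.** With the experimental arm at the margin (4% at five years) and the same mortality in both arms, Kaplan-Meier gives a difference of 4.00 − 2.00 = 2.00 points. Cumulative incidence gives 3.90 − 1.95 = 1.95 points with 5% dead, and 3.80 − 1.90 = 1.90 points with 10% dead. Kaplan-Meier therefore makes omission look very slightly worse than it is.

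**The case against.** The strongest objection is that handling of deaths in a secondary outcome is ordinary content for a statistical analysis plan, that no sentence in the protocol says deaths are censored, and that the effect is trivial. Much of this stands. Censoring is inferred from the definition rather than written. The five-year excess of 0.05 to 0.10 points is small beside the 2-point margin and beside the standard error of a difference at 2% with 950 per arm, √(2 × 0.02 × 0.98/950) = 0.64 points. Even 10% dead by five years would require every control-arm DFS event by then to be in a participant who has died. What does not stand is that this is mere silence: section 10.3.3 names the estimator without exception, and a later plan that follows it would apply Kaplan-Meier to ARFI.

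A reader might also infer more than the documents support:

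- **That all site-specific events are to be summarised by Kaplan-Meier.** Section 3.2.2 defines local, regional, distant, contralateral and non-breast events as events, with no interval and no censor date. The method is not expressly assigned to them.
- **That Kaplan-Meier makes the site-specific risks sum to more than the risk of any event.** Axillary recurrence as defined is a subset of regional recurrence, and one participant can have several event types. These risks overlap under any estimator, and the protocol does not add them.
- **That the economic results would be biased.** The within-trial analysis in section 10.4 uses frequencies of recurrence, and the form of the long-term model is still undecided. A model that handles death separately would need cause-specific rates.
- **That the trial's conclusion is at risk.** Section 10.3.3 rests success on DFS and lymphoedema, neither of which is touched.

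**Conclusion.** The point holds for ARFI and is minor. Sections 3.2.2 and 10.3.3 read together lead to Kaplan-Meier with deaths censored, and its complement exceeds the actual risk of axillary recurrence: by at most about 0.10 points on 2.00% at five years, and by 0.18 to 0.35 points on 3.77% at 9.5 years. These figures rest on assumed mortality of 5% to 10% by five years, constant hazards, deaths independent of axillary recurrence, and the planned 98% read as the Kaplan-Meier value.

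The Cox model remains a valid cause-specific comparison. The effect is conservative for non-inferiority provided mortality is similar in the two arms.

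**What to change.** In section 3.2.2, state that a participant who dies without axillary recurrence has a competing event, and define the censor date.

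In section 10.3.3, add wording such as: for ARFI, and for any other site-specific outcome (local, regional, distant, contralateral or non-breast) that is analysed over time, the five-year risk and the difference between arms will be estimated by cumulative incidence (Aalen-Johansen) with death as a competing event, alongside the cause-specific Cox model. Keep Kaplan-Meier for DFS and overall survival.

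The cost is a few sentences and standard software, with no new data and no change to the sample size. Carry the same wording into the statistical analysis plan before the final analysis, so that the choice between two estimates of the same risk is not made after the results are seen.
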